## **13.4 Permission to Review Source Records**

In accordance with the European Guidelines on Good Clinical Research Practice, it is desirable to check case report forms against original patient records. Therefore, the investigator agrees that the sponsor, the sponsor's representatives, the CRO, its employees or agents will have the right to audit and review pertinent medical records relating to this clinical trial.

## **13.5 Unanticipated Events**

Any changes in the study or unanticipated events involving risks to the subjects must be reported promptly to the Ethics Committees.

## 13.6 Privacy and Confidentiality

A subject's privacy and confidentiality will be respected throughout the study. Each subject will be assigned a sequential identification number, and these numbers rather than names will be used to collect, store, and report subject information.

## **14. PUBLICATION POLICY**

The CIT policy on the publication of study results will apply to this trial.

## **APPENDIX 1: SCHEDULE OF EVENTS**

							DAY					MC	NTH	1 Yr post 1 st Tx 
Time points	Screen	WL	BL	Transplant	1	3	7	14	21	28	75 	6	12	
Visit Number	01		02	03	04	05	06	07	08	09	10	11	12	Y1
Visit Windows (Days)	N/A			±0	±0	±0	±3	±3	±3	±3	±5	±14	±14	±14
(2 4 5 5)			CEN	JERAL ASSES										
Informed consent	X		ULI											
Evaluation of Eligibility Criteria	X		X											
Quality of Life (SF36, DTSQ) 	X	Х									X 1		X	Х
Medical and Diabetes History	X													-
Retinopathy Evaluation	X	Х												Х
Physical Exam and Vital Signs (Weight, Height  , BMI  , Temperature,	x	x	x	x	x	x	x	x	x	x	x	x	x	x
Pulse, Blood Pressure)	X	Х	X											
Chest X-Ray	X	Λ	Λ	X	X									
Abdominal Ultrasound	-			^	Λ									
ECG, Myocardial Scintigram	Х	X4	X4											
Conduction Velocity and RR intervals	Х												Х	Х
Immunosuppression Medications				$\rightarrow$	$\rightarrow$	$\rightarrow$	$\rightarrow$	$\rightarrow$	$\rightarrow$	$\rightarrow$	$\rightarrow$	$\rightarrow$	$\rightarrow$	$\rightarrow$
Concomitant Medications			$\rightarrow$	$\rightarrow$	$\rightarrow$	$\rightarrow$	$\rightarrow$	$\rightarrow$	$\rightarrow$	$\rightarrow$	$\rightarrow$	$\rightarrow$	$\rightarrow$	$\rightarrow$
Assessment of AE, SAE, Infections, Hospitalizations, Rejections	$\rightarrow$	$\rightarrow$	$\rightarrow$	$\rightarrow$	$\rightarrow$	$\rightarrow$	$\rightarrow$	$\rightarrow$	$\rightarrow$	$\rightarrow$	$\rightarrow$	$\rightarrow$	$\rightarrow$	$\rightarrow$
Blood Sugar Record eCRF	X5	X5	X5								X5	Χ5	X5	X5
Glucometer Download	X5	Χ5	X5	X5			Х	Х	X	Х	X5	X5	X5	X5
Insulin Requirement (Total U/24 h) 	X 	X 	X 	X 			X	X	X	X	X 	X 	X 	X 
Portal Pressure				X 6										
	•	LOC	CAL LA	BORATORY	ASSES	SMEN	NTS	•						
HLA, Blood Type	Х													
Cross Match			Х											
CBC with differential 	Х	Х	Х	X 7	X 7	X 7	Х	X 7	X 7	Х	Х	Х	Х	Х
Serum chemistry panel  and CRP	x	Х	Х	X	Х	Х	Х	Х	Х	Х	Х	Х	х	Х
Coagulation Status (APTT, PK, fibrinogen, platelets)	х	Х9	x	Х9	x	x	x	x	x	x	х		х	x
Urine Albumin	Х										Х		Х	Х
Fasting Lipid Profile (Total, LDL, HDL, Triglycerides)	х			х						x	x	x	х	х
Glomerular Filtration Rate (GFR)	Х										X 10		Х	Х
Serum Pregnancy Test	Х		X11											-
Fast. & Postprandial Plasma Glucose						X	X	X	X	X12				-
Fasting & post-prandial C peptide	Х	X13	X13			Х	X	Х	Х	X12			X	
HIV, Hepatitis B, Hepatitis C 		Λ1.5	Λ 											-
CMV IgG, IgM	X												Х	
EBV IgG	Х													
CMV by PCR			Х								Х	Х		
EBV by PCR			Х											
		IMMU	INOSU	PPRESSION	ΓROU	GH LI	EVELS							
Tacrolimus Or Cyclosporine Levels 				Х	Х	Х	Х	Х	Х	Х	Х	Х	Х	Х
Sirolimus Levels 14				Х	Х	Х	Х	Х	Х	Х	Х	Х	Х	Х
			S	TUDY TREAT	MENT	[								
Islet Transplant Waiting List		Х												
Identify Compatible Donor		Х												
Randomization				X										
Refer to section 7.2 W Assess				t Assessment							e WL	perioc	1.	

Clinical Islet Transplantation Protocol CIT-01

	Pre-Transplant			DAY								MONTH		1 Yr post
Time points	Screen	WL	BL	Transplant 	1	3	7	14	21	28	75 	6	12	1 st Tx 
Visit Number	01	0	)2	03	04	05	06	07	08	09	10	11	12	Y1
Visit Windows (Days)	N/A			±0	±0	±0	±3	±3	±3	±3	±5	±14	±14	±14
		CEN	JTRA	L METABOL	IC ASS	ESSM	IENTS							
HbA1C (%) 	Х	Х	Х							Х	Х	Х	Х	Х
Mixed-Meal Tolerance Test 	Х										Х	Х	Х	Х
Insulin Modified FSIGT test 	Х										X 1		Х	Х
	(	CALC	ULAT	ED METABC	DLIC AS	SSESS	MEN	ГS						
Glycemic Lability (MAGE)		X 5									X 1		Х	Х
Glycemic Lability (LI)	Х	X25									X 1		Х	Х
Full HYPO Score	Х	X25									X 1		Х	Х
Clarke Score	Х	Х									X 1		Х	Х
β-Score 											Х	Х	Х	Х
C-Peptide to Glucose, Creatinine Ratio 	Х										Х	Х	Х	Х
		L	OCAL	METABLOI	C ASSE	SSMI	ENT							
Positron Emissions Tomography (PET) 				Х										
Continuous Glucose Monitoring System ®	Х	Х									X 1		Х	Х
			Ν	IECHANISTI	C ASS	AYS								
Alloantibodies 	Х	Х	Х	_							X20	X20	X20	X 
Autoantibodies (GAD, IA2, IAA) 			Х								Х	Х	Х	Х
TAT Complex, C-peptide, and C3a 				Х	Х									
			A	RCHIVED SI	PECIMI	ENS								
Serum 	Х										Х	Х	Х	
PBMC and Plasma 	Х										Х	Х	Х	
RNA 	Х										Х	Х	Х	
RNA and Plasma 			Х			Х		Х			Х			Х
Refer to section 7.2	2 Wait List	/ Base	eline V	visit Assessme	nts for	freque	ency of	testing	g durin	g the V	NL per	iod.		

1 DAY 75 (Primary Endpoint): If needed, repeated transplant(s) will be performed more than 75 days after the first transplantation. The previous follow-up period stops and a new visit period starts, beginning with the baseline visit. After a second or third transplant the 75 day follow up will NOT include QoL Surveys, MAGE, LI, CLARKE, HYPO, FSIGT, or CGMS.

2 YEAR 1 POST INITIAL TRANSPLANT: If 1-year post initial transplant (Visit Y1) falls within a visit window of a scheduled re-transplant study visit, complete only the eCRFs for the 1-year post initial transplant visit. If Y1 visit does not fall within a re-transplant visit, complete the Y1 visit in addition to the scheduled re-transplant visit.

3 Height and BMI assessment completed at screen, baseline and 12 months only.

4 Myocardial Scintigram not required at visit 02.

5 Diary Log eCRF completion is completed using blood sugar record, hypo sheets, glucometer download, and insulin requirements, this is required at each visit.

6 Portal pressure: Before islet infusion, and 15 minutes after completion of the islet transplant.

7 The CBC with differential should be completed within 2-hours prior to planned transplant. Differential not required at the following visits: 04, 05, 07, and 08

8 Sodium, Potassium, Creatinine, Glucose, Albumin, Alk Phos, ALT, AST, LDH, T. Bilirubin

9 Coagulation status must be normal prior to transplant. Hemoglobin should be monitored before, immediately after, four hours after islet transplant, and 2 hours after removal of the portal catheter. CVP should be measured before and after placement of the portal catheter. Blood pressure and pulse should be monitored continuously until 4 hours post removal of portal catheter. During treatment with LMW-DS or heparin, APTT will be monitored.

10 GFR completed at screening and at 75 days (+/- 5 days) after the FIRST islet transplant, and 365 days (+/- 14 days) after first and final islet transplant.

11 Pregnancy test within 3 days of randomization

12 Before and after breakfast. No insulin before the second measurement.

13 Serology panel include s HBcAb, HBsAg, HBsAb, HCV Ab, HIV. Do not repeat Hepatitis B tests if HBsAb was previously positive.

14 Applicable immunosuppression levels.

15 Total daily dose (IU), day before visit (24 h)

16 Central laboratory assessment: University of Washington (Seattle, WA)

17 Results based on the HbA1c, Insulin requirement, and fasting (basal) serum glucose and stimulated C-peptide from the MMTT (Ryan, et al)

18 Results based on the fasting (basal) serum glucose and c-peptide from the MMTT and the simultaneous serum creatinine.

19 This is a substudy to be completed in a subset of subjects (n=8, 4 LMW-DS, 4 Control) at selected sites.

20 Central Laboratory assessment: U. Pennsylvania (Philadelphia, PA)

21 Central laboratory assessment: The Barbara Davis Center Laboratory (Denver, CO)

22 Central laboratory assessment: The Rudbeck laboratory (Uppsala, Sweden)

23 Central Laboratory: The NIDDK Repository

24 Only SF36 completed during the baseline / wait list visits. DTSQs completed during the screening visit and DTSQc completed at the 12 month post first and final islet transplant.

25. Repeat the LI or HYPO during the Baseline/Waitlist period only if the inclusion criteria for study enrollment (inclusion criteria #7b or #7c) were used for inclusion in the study.

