The resistance of islet-directed autoimmune responses to conventional immunosuppressive drugs (65-69) and the immediate exposure of intraportally transplanted islets to primed autoreactive, islet beta celldirected T cells provide a strong rationale for pre-transplant initiation of ATG, which is known to cause selective depletion of activated T cells and dose-dependent depletion of resting T cells (70). Experimental data suggest that the protection of whole pancreas transplants from recurrent autoimmunity is functionally related to the inclusion of a significant quantity of lymphoid tissue (possibly containing an immunoregulatory T cell subset) as part of the pancreas graft and not to immunosuppression alone (71, 72). Clinical evidence also indicates that destructive anti-islet autoimmunity persists for decades after manifestation of T1D (66, 73, 74) and that type 1 diabetic individuals with long disease duration do not spontaneously anergize their autoreactive effector Th1 cells and/or restore Th2 or other regulatory T cell function. Accordingly, reprogramming the recipient's immune system seems to be of paramount importance if autoimmune recurrence in transplanted islets is to be prevented.

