### 4.1.4 Safety Endpoints

### At 75 $\pm$ 5 days and 365 $\pm$ 14 days following the first islet infusion:

- The incidence and severity of adverse events related to the islet infusion procedure including: bleeding (> 2 g/dl (20g/L) decrease in hemoglobin concentration); segmental portal vein thrombosis; biliary puncture; wound complication (infection or subsequent hernia); and increased transaminase levels (> 5 times ULN)
- The incidence and severity of adverse events related to the immunosuppression including: allergy; reduction in GFR; increase in urinary albumin excretion; addition or intensification of anti-hypertensive therapy; addition or intensification of anti-hyperlipidemic therapy; oral ulcers; lower extremity edema; gastrointestinal toxicity; neutropenia, anemia, or thrombocytopenia; viral, bacterial, or fungal infections; and benign or malignant neoplasms
- The incidence of immune sensitization defined by detecting anti-HLA antibodies not present prior to transplantation
- The incidence of a change in the immunosuppression drug regimen

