# 5.5 RABBIT ANTI-THYMOCYTE GLOBULIN (ATG, THYMOGLOBULIN®)

A total of 6 mg/kg will be given as an IV infusion on days -2, -1, 0, +1, and +2. The dose will be 0.5 mg/kg on day -2, 1.0 mg/kg on day -1, and 1.5 mg/kg on days 0, +1, and +2. The first dose will be administered over 6-12 hours and subsequent doses will be administered over 6 hours. If, for practical reasons, three doses can not be administered before transplantation the first and second will be administered on day -1 and 0 and the three remaining will be administered on day +1, +2 and +3. At least six hours between each infusion and also between infusion and transplantation is recommended.

Premedications will be used as follows:

#1: Paracetamol (i e Alvedon®) 1000 mg PO/PR ½ hr before and midway through the ATG infusion #2: Klemastin (Tavegyl®) 1 mg PO ½ hr before and midway through the ATG infusion. Alternatively 5 mg Dexchlorpheniramine® is administered IV ½ hr before the ATG infusion

#3: Methylprednisolone (Solu-Medrol®) 1 mg/kg IV one hour prior to and as needed during the first ATG infusion only (*i.e.*, on day –2)

Time	Sample Day	Sample Time	Activity
0 hour	Day -2	1600	Viable islet prep into culture
0-12 hours	Day -2/Day-1	1600-0400	ATG #1 over 6-12 hours
12-18 hours	Day -1	0400-1000	Rest for 6 hours
18-24 hours	Day -1	1000-1600	ATG #2 over 6 hours
24-32 hours	Day -1	1600-2400	Rest for 8 hours
32-38 hours	Day 0	2400-0600	ATG #3 over 6 hours
38-44 hours	Day 0	0600-1200	Preparations for Transplant
44 hours	Day 0	1200	Islet Transplant

Three pre-transplant infusions of ATG are suggested to be administered according to the following algorithm.

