#### 5.15.2.3 NEUTROPENIA

Neutropenia is an expected consequence of the administration of several medications in this protocol. Subject safety is of utmost importance. Clinical treatment decisions take precedence over recommended guidelines.

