# If a subject's absolute neutrophil count is less than 1000 cells/ $\mu$ L and the subject is afebrile, then the following will be done:

- Reduce rabbit ATG by 50%.
- Reduce the prophylactic use of valganciclovir from 900 mg per day to 450 mg per day or hold valganciclovir.
- Reduce trimethoprim/sulfamethoxazole to 80/400 mg on Monday, Wednesday, and Friday or hold trimethoprim/sulfamethoxazole.
- Review and obtain current sirolimus trough levels and consider dosage adjustment if trough level are >12ng/mL.
- If subject is using mycophenolate mofetil or mycophenolate sodium in lieu of sirolimus, consider dose reduction.
- Consider administration of G-CSF.
- Monitor temperature BID.
- Follow up within 48-72 hours to obtain: repeat complete blood count (CBC) with differential, subject symptoms, and measured temperatures.

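### The schedule waives the white-cell differential at Days 1, 3, 14 and 21, leaving neutrophil counts required only at Days 7 and 28 after transplant, although several drugs are adjusted by that count

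*Protocol*

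**What the plan says.** The neutropenia section of the protocol (5.15.2.3; the same number is used again for nephrotoxicity) opens by stating: "Neutropenia is an expected consequence of the administration of several medications in this protocol". Its rules start when a subject's "absolute neutrophil count is less than 1000 cells"/µL, with stricter steps below 500, and each level is split by presence or absence of fever. The actions cover ATG, valganciclovir, trimethoprim-sulfamethoxazole, sirolimus, MMF and G-CSF. Once a count below 1000 is known, the afebrile rule orders: "Follow up within 48-72 hours to obtain: repeat complete blood count (CBC) with differential".

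In Appendix 1 the row for the blood count with differential is marked at every visit. Footnote 7 asks for the full count with differential in the two hours before transplant and then adds: "Differential not required at the following visits: 04, 05, 07, and 08".

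Section 5.5 gives ATG at "1.5 mg/kg on days 0, +1, and +2" after two smaller doses. In a fallback schedule two doses precede transplant and "the three remaining will be administered on day +1, +2 and +3". Section 4.1.4 lists "neutropenia, anemia, or thrombocytopenia" among the events counted for incidence and severity.

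**The concern.** The rules act on a measurement that the schedule does not require at most of the visits where it would be used. The afebrile rules matter most here: a patient without fever gives no clinical prompt, so only a neutrophil count can identify the need to cut ATG, hold valganciclovir or give G-CSF.

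The total white count, still obtained at each visit, is a partial substitute. A total below 1000 cells/µL proves that the neutrophils are below 1000. A higher total does not exclude it. Section 1.2.3 on induction therapy describes ATG as "known to cause selective depletion of activated T cells", so a falling total after ATG does not show which cell line is falling.

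The neighbouring thrombocytopenia rule shows the contrast. It also adjusts ATG and sirolimus, and platelets are scheduled at every visit through Day 28. Sirolimus troughs, another input to the neutropenia rule, are scheduled at each of these visits too. Only the count that starts the neutropenia rule is waived.

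At stake are timely drug adjustment during the period of heaviest immunosuppression and complete recording of neutropenia as a safety endpoint.

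**Working it through.** The plan states no figure for this point, so the check is a count of visits and gaps.

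**Inputs.** Visit numbers, days and windows come from Section 7.7 (Table 4) and the Appendix 1 header. The waiver comes from footnote 7, and the ATG days from Section 5.5.

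| Visit | Day (window) | CBC drawn | Differential required now | With the waiver deleted |
|---|---|---|---|---|
| 03 | 0 (±0) | yes | yes | yes |
| 04 | 1 (±0) | yes | no | yes |
| 05 | 3 (±0) | yes | no | yes |
| 06 | 7 (±3) | yes | yes | yes |
| 07 | 14 (±3) | yes | no | yes |
| 08 | 21 (±3) | yes | no | yes |
| 09 | 28 (±3) | yes | yes | yes |

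**Required counts on Days 1 to 28.** Now: 6 − 4 = 2 of 6. With the waiver deleted: 6 of 6.

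**Gaps now.**
- Day 0 to Day 7: nominal 7 days; range 7 − 3 = 4 to 7 + 3 = 10.
- Day 7 to Day 28: nominal 28 − 7 = 21 days; shortest 25 − 10 = 15; longest 31 − 4 = 27.

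**Gaps with the waiver deleted.** Nominal gaps are 1, 2, 4, 7, 7 and 7 days, so the longest is 7. At the widest windows a weekly gap can reach, for example, Day 4 to Day 17 = 13 days.

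**Longest neutropenia lying wholly between two required counts (whole days).**
- Now: Days 8 to 27 = 20 days nominal; Days 5 to 30 = 26 days at the widest windows.
- With the waiver deleted: 7 − 1 = 6 days nominal; Days 5 to 16 = 12 days at the widest windows.

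**ATG doses against counts.** The Day 0 count follows two or three ATG doses and can guide the next ones. The standard schedule then gives 1.5 + 1.5 = 3.0 of 6.0 mg/kg on Days +1 and +2. The fallback gives three doses on Days +1 to +3 (1.5 + 1.5 + 1.5 = 4.5 of 6.0 mg/kg, assuming the dose order is kept). The next required count is at Day 7, or Day 4 at the earliest, after the last dose in both schedules. A Day 1 differential could change an ATG dose; a Day 3 differential could do so only in the fallback.

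**Other drugs.** MMF or sirolimus runs throughout the study, valganciclovir for 3 months and trimethoprim-sulfamethoxazole (where it is the chosen prophylaxis) for 6 months (Sections 5.7 and 5.10). All therefore continue across the Day 7 to Day 28 gap.

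**Later transplants.** Section 7.5 restarts the visit schedule at each infusion, but ATG is normally given only at the first. After later transplants only the Day 7 to Day 28 gap for the other drugs matters.

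**The case against.** The best case for leaving the footnote alone is that other safeguards surround it.

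- The waiver is a floor, not a ban, and a site may run the differential anyway. True, but detection then depends on local habit across 7 centers.
- Section 8.2.1 requires an abnormal laboratory result that may indicate an adverse event to be repeated or explained, and Sections 5.7.1 and 5.7.2 allow MMF and sirolimus to be adjusted for leukopenia. Both act on the total white count. They narrow the gap, but they do nothing when the total looks unremarkable, and a low total may be put down to ATG's effect on lymphocytes.
- A patient already known to be low at Day 0 or Day 7 enters the triggered follow-up. This stands. The 20- and 26-day figures concern only neutropenia that begins after a count of at least 1000 at Day 7, as an episode lying wholly between counts implies.
- The ATG part is thin, because a count precedes the Day +1 dose and few later doses could change. This also stands. The longer gap for the other drugs carries more weight.
- The rules leave room for clinical judgement, and Section 5.15.1 lets the investigator modify immunosuppression. But judgement about neutropenia still needs the count.
- The gap figures describe the calendar, not harm. That is correct: the protocol gives no basis for a number of missed episodes.

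**Conclusion.** The point holds. After the Day 0 count, the protocol requires a neutrophil count at 2 of 6 visits through Day 28, with a longest gap of 21 days nominal (15 to 27 with windows), while it ties drug actions to that count and calls neutropenia expected. The triggered repeat counts do not fill the gap, because they start only after a low count has been found.

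The figures rest on the scheduled minimum: visits within their windows and no optional differentials. They need no assumption about when neutropenia starts or how long it lasts, and they do not estimate how many episodes would be missed.

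The consequence is for patient safety and for the completeness of the neutropenia endpoint. Both arms follow the same schedule, so the primary endpoint and the treatment comparison are not affected. It is a modest weakness, worth correcting because the remedy is so cheap.

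**What to change.** Delete from footnote 7 of Appendix 1 the sentence "Differential not required at the following visits: 04, 05, 07, and 08", so that the differential is reported from the blood count already drawn at each visit. The Day 1 result (and Day 3 in the fallback) then serves the ATG rules. Days 14 and 21 serve the rules for the other drugs and the neutropenia endpoint. The drug rules themselves need no change.

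The cost is one sentence in a footnote and four routine differentials per infusion, with no extra visit or blood draw.

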## APPENDIX 2. REDUCED FOLLOW-UP SCHEDULE

Subjects withdrawn from study therapy should be followed according to the reduced follow-up schedule provided below. All reduced follow-up assessments should be scheduled relative to the day on which the study treatment is discontinued. The last follow-up visit will vary depending on when the subject discontinues study therapy and should be done at 1-year post the subject's **last** transplant.

Complete the following assessments at the intervals (+/- 7 days) indicated below relative to the day the subject discontinued study treatment. Continue conducting these assessments at the defined intervals until the subject reaches one year post **last** transplant.

- Assess SAEs and hypoglycemic events: q1 month. If subject does not come to the study site for the visit, attempt to obtain information via a phone contact.
- Alloantibody (central lab): q 1 month for the first 3 months and q 3 months thereafter.

Complete the following assessments at 1-year (+/- 14 days) post initial transplant:

- Assess SAEs and hypoglycemic events
- Alloantibody (central lab)
- HbA1c (central lab)
- 90 minute c-peptide post MMTT (central lab)
- Serum creatinine (central lab)
- QOL questionnaire (via mail or in-person)

Complete the following assessments at 1-year (+/- 7 days) post **last** transplant:

- Assess SAEs and hypoglycemic events
- QOL questionnaire (via mail or in-person)

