### At 365 ± 14 days following the first islet infusion:

• The incidence of worsening retinopathy as assessed by change in retinal photography from pretransplant to 365 ± 14 days following the first islet infusion. If pupil dilation is not possible, then a manual ophthalmologic exam can be substituted.

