## 5.15.3 Premature Discontinuation of Study Treatment

Study treatment may be prematurely discontinued for any subject for any of the following reasons:1.

The subject is unwilling or unable to comply with the protocol.2. The investigator believes that the study treatment is no longer in the best interest of the subject.3. Graft Failure: Islet allograft failure will be defined as absence of insulin production by transplanted islets, as evidenced by absence of c-peptide <0.1nmol/L (<0.3 ng/mL). This will be determined by (1) c-peptide <0.1nmol/L (<0.3 ng/mL) on random testing, followed by (2) c-peptide<0.1nmol/L (<0.3 ng/mL) at baseline, and at 60 and 90 minutes after MMTT. C-peptide levels obtained in the course of the MMTT levels will be run at the core laboratory in Seattle, WA. Subjects with graft failure do not need to complete the day 75 metabolic assessments.

4. A unexpected related serious adverse event. The agent(s) to which the event is attributed will be discontinued.

Subjects who prematurely discontinue study treatment will remain in the study until normal termination, for the purpose of monitoring safety and efficacy parameters and will enter the reduced

schedule outlined in Appendix 2. Data from these subjects will be used in the intent-to-treat analysis. 6. Criteria for Premature Termination of the Study

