## 7.5 Follow Up Schedule and Procedures

Subjects will undergo clinical evaluation by the investigator and/or their designee at screening, baseline, transplantation, days 1, 3, 7, 14, 21, 28, 75, and months 6 and 12 (Appendix 1). Clinical safety will be monitored through routine physical examinations and appropriate laboratory assessments. During the study, subjects will have repeated clinical and laboratory evaluations, as specified in the Schedule of Events. The timing of all follow-up assessments will reset at the time of subsequent transplants (i.e., the day of the second transplant becomes day 0, and all assessments are conducted in relation to this day).

Evaluations should be made for sirolimus, cyclosporine and tacrolimus levels, as applicable. Immunosuppression levels will be monitored from time of transplantation until the end of the study.

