## 8.2 Adverse Events 8.2.1 Collecting Procedure

AEs that are associated with a protocol-mandated procedure, that is not part of the normal standard of care, and hypoglycemic events will be collected beginning immediately after the consent document has been obtained. All other AEs will be collected immediately after randomization. All AEs will continue to be collected until study completion, or for 30 days after the subject prematurely withdraws from the study. AEs will be followed until the time the event is resolved, stabilized, or the participant completes or withdraws from the study, whichever occurs first.

AEs may be discovered through any of these methods:

- Observing the subject.
- Questioning the subject, this should be done in an objective manner.
- Receiving an unsolicited complaint from the subject.
- An abnormal value or result from a clinical or laboratory evaluation (e.g., a radiograph, an ultrasound, or an electrocardiogram) can also indicate an AE. If this is the case, then the evaluation that produced the value or result should be repeated until the value or result returns to normal or can be explained and the subject's safety is not at risk. If an abnormal value or result is determined by the investigator to be clinically significant, it must be reported as an AE.

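### Appendix 2 omits non-serious adverse events in subjects who stop study treatment, although sections 5.15.3 and 8.2.1 keep them under AE collection to study completion

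*Protocol*

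**What the plan says.** Section 5.15.3 states: "Subjects who prematurely discontinue study treatment will remain in the study until normal termination, for the purpose of monitoring safety and efficacy parameters". The same sentence goes on to place these subjects on the reduced schedule of Appendix 2. One of the listed reasons for stopping is an unexpected related serious adverse event, and there the consequence is limited: "The agent(s) to which the event is attributed will be discontinued".

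Section 8.2.1 sets the general collection rule: "All AEs will continue to be collected until study completion, or for 30 days after the subject prematurely withdraws from the study". Section 8.3.1 limits reporting to grade 2 and above.

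For clinical events Appendix 2 says: "Assess SAEs and hypoglycemic events: q1 month". It repeats that restriction at the two 1-year contacts. It also collects other data: "Alloantibody (central lab): q 1 month for the first 3 months and q 3 months thereafter", and at 1 year after the first transplant HbA1c, 90-minute C-peptide, serum creatinine and quality of life.

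Section 7.4.2 adds a second way in: subjects who do not meet the criteria for a subsequent transplant also go to Appendix 2.

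Section 7.5 says: "Immunosuppression levels will be monitored from time of transplantation until the end of the study". The sentence before it limits the measurement to the drugs that apply. Appendix 2 lists no drug levels.

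**The concern.** Safety is part of the primary objective (section 2.1), and section 4.1.4 assesses safety endpoints at day 75 and day 365 after the first infusion. Many of these are not serious events by nature: cytopenias, a fall in GFR, a rise in urinary albumin, added or intensified anti-hypertensive or lipid therapy, oral ulcers, edema and non-serious infections. A further one is "The incidence of worsening retinopathy as assessed by change in retinal photography" from before transplant to day 365.

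A site that follows Appendix 2 will not record the non-serious events and will not make most of the measurements. A site that follows section 8.2.1 will record the events. Sites may therefore differ in what they collect, and no later analysis plan can recover data that were never collected.

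**Working it through.** The protocol gives no figure on this point, so the check is mainly a comparison of texts.

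**Step 1: does an exception in section 8.2.1 remove the conflict?** Its 30-day limit applies to subjects who withdraw from the study. Section 5.15.3 says that subjects who stop treatment remain in the study. The exception does not reach them, so the rule for them is collection to study completion. Appendix 2 asks for less.

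**Step 2: which day-365 safety endpoints lose their data source?** Visit Y1 in Appendix 1 is set against Appendix 2:

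| Endpoint in 4.1.4 | Appendix 1, visit Y1 | Appendix 2 |
|---|---|---|
| Non-serious grade 2+ AEs (oral ulcers, edema, infections) | AE assessment | none (SAEs and hypoglycemia only) |
| Neutropenia, anemia, thrombocytopenia | CBC | none |
| Reduction in GFR | GFR | one serum creatinine at 1 year |
| Urinary albumin | urine albumin | none |
| Added anti-hypertensive or lipid therapy | concomitant medications | none |
| Worsening retinopathy | retinopathy evaluation | none |
| Immune sensitization | alloantibodies | alloantibodies, more often |

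Immune sensitization is fully covered and GFR only indirectly. The others are not covered unless the event is serious.

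**Step 3: is the drug-level conflict real?** Only for subjects still taking a monitored drug. The protocol creates such subjects in three ways: only the attributed agent stops after an unexpected related SAE (5.15.3); immunosuppression continues for a time and is then tapered after primary non-function (6.3); and the route in 7.4.2 has no link to stopping immunosuppression. For anyone no longer taking these drugs there is nothing to measure and no conflict.

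**Step 4: what could this do to an incidence?** All inputs except the arm size are assumptions. Let n = 18 per arm (10.4), k = 2 to 6 subjects in the arm on the reduced schedule, p = 0.30 or 0.60 the true day-365 incidence, and s = 0.5 to 1.0 the share of those subjects' events that arise after the switch.

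- Unrecorded events counted as none: [(18 − k)p + k·p·(1 − s)]/18.
  - p = 0.30: k = 2, s = 0.5 gives 5.1/18 = 0.28; k = 6, s = 1.0 gives 3.6/18 = 0.20.
  - p = 0.60: 10.2/18 = 0.57 down to 7.2/18 = 0.40.
- Failure imputed for those k subjects, as section 10.2.2 does for an unevaluated dichotomous endpoint: [(18 − k)p + k]/18.
  - p = 0.30: k = 2 gives 6.8/18 = 0.38; k = 6 gives 9.6/18 = 0.53.
  - p = 0.60: 11.6/18 = 0.64 up to 13.2/18 = 0.73.

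The same gap pulls the estimate down under one rule and up under the other. The synopsis labels these safety endpoints as secondary, but section 10.2.2 does not say whether its imputation rule covers AE incidence.

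**The case against.** **The reduced schedule is deliberate.** Section 5.15.3 adopts Appendix 2 in the very sentence that keeps subjects in the study, and lighter follow-up after stopping treatment is a legitimate choice. That stands, and it is a reason not to insist on every Appendix 1 procedure. It does not remove the conflict with section 8.2.1, which makes no exception for these subjects.

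**Late events say little about the randomized comparison.** LMW-DS is given for no more than 6 hours and both arms follow the same immunosuppression protocol. Transaminase rises belong to the infusion procedure, and liver enzymes are measured one and seven days after each transplant, so most would be seen before any switch. This stands in part: it limits the damage to the arm comparison, and transaminases are left out of the point. But the protocol itself names the other events as day-365 safety endpoints.

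**Stronger readings that the text does not support.**
- A reader might infer that missing events are scored as absent, so that the arm with more discontinuations looks safer. No passage says so, and the only related rule imputes failure. How missing safety data are tabulated may also be settled in the SAP, which is not at hand.
- A reader might infer that these are the sickest subjects. The entry reasons also include non-compliance, the investigator's judgment, graft failure and not qualifying for another transplant, and SAEs are still collected in all of them.
- A reader might say that the schedule records nothing but SAEs and hypoglycemia. That is true of clinical events only.
- A reader might take section 7.5 as requiring levels in everyone to study end. Its restriction to applicable drugs rules that out.

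**Conclusion.** The conflict is plain in the text. For subjects who stop treatment but remain in the study, section 8.2.1 requires all AEs and Appendix 2 asks only for SAEs and hypoglycemic events. Non-serious events of grade 2 or higher, and the day-365 endpoints on cytopenias, GFR, urinary albumin, added therapy and retinopathy, cannot be fully ascertained in them.

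The size depends on how many subjects enter the schedule, which the protocol does not predict. Each is 5.6% of an arm, and how widely section 7.4.2 is meant to reach is unclear. The ranges in the illustration rest on assumed values of k, p and s, and the direction of any bias is not fixed. The drug-level conflict is narrower and holds only for subjects still taking immunosuppression. This should be corrected, and the part that matters most is cheap to correct.

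**What to change.** 1. Amend Appendix 2 to agree with section 8.2.1: at the monthly contact already planned, record all reportable (grade 2 or higher) AEs and the relevant concomitant medication changes (anti-hypertensive, lipid-lowering, immunosuppressive), not only SAEs and hypoglycemia.
2. In the day-365 safety tables, give the number assessed for each endpoint and show subjects without an assessment as not assessed rather than event-free. State whether the failure imputation in section 10.2.2 applies to AE incidence.
3. Reconcile section 7.5 with Appendix 2 on drug levels for subjects still taking immunosuppression, and say which subjects section 7.4.2 means to send to the reduced schedule. What monitoring these subjects receive is a clinical decision for the sponsor and investigators; the two texts only need to agree.

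The cost is an amendment to one appendix with matching wording in sections 7.4.2 and 7.5, and a few more questions at a contact that already takes place and may be by telephone. The change in item 1 needs no new procedure. Adding retinal, GFR or urine albumin assessments at the existing 1-year visit would close more of the gap, but is optional; without them, item 2 makes the gap visible.
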